9.2. Exclusion Criteria

1. Patients with DSM-V criteria at the first Screening Visit (Week -5) for disorders other than schizophrenia that in the opinion of the Investigator may interfere with study conduct and interpretation of results.
2. Patients who, in the opinion of the Investigator, have a history of antipsychotic treatment resistance.
3. Patients currently taking clozapine.
4. Patients who have been previously treated with or are receiving electroconvulsive therapy (ECT).
5. Patients who have initiated or changed dose of antidepressants or other mood stabilizers within 7 weeks prior to the first Screening Visit (Week -5).
6. Patients currently taking lithium.
7. Patients taking an AP (e.g. Seroquel) as a sleep aid.

Note: Patients will be allowed to switch to a non-AP sleep aid during the Screening period.

8. Patients who use prescription medications (stimulants) to treat attention deficit hyperactivity disorder or attention deficit disorder.
9. Screening laboratory measurements outside the normal range associated with potential risk for the treatment under investigation at the first Screening Visit (Week -5). This will include but not limited to:
 - a. Aspartate transaminase (AST), alanine transaminase (ALT), gamma-glutamyl transferase (GGT), or total bilirubin > 2x upper limit of normal (ULN)
 - b. Estimated glomerular filtration rate (eGFR) < 60 mL/minute/1.73 m²
 - c. Serum creatinine and/or blood urea nitrogen (BUN) > ULN
 - d. Urinalysis positive for protein or urine microalbumin/creatinine ratio (UACR) > 30 mg/g

Note: These laboratory tests may be repeated once, if they are abnormal on first screening, and if there is a medical/analytical reason to believe the results may be inaccurate. If the repeat test is within the reference range, the patient may be included only if the Investigator considers that the previous finding will not compromise the patient's safety and will not interfere with the interpretation of safety data.

10. Patients with suicidal behavior occurring within the past year or who pose a current suicide risk as determined by the PI or as confirmed at the first Screening Visit (Week -5), the Qualification Visit (Week -3) or Day -1 by affirmative answer on items 4 or 5 on the Columbia-Suicide Severity Rating Scale (C-SSRS).
11. Treatment with an investigational drug within 7 weeks or 5 half-lives (if known), whichever is longer, prior to the first Screening Visit (Week -5).
12. Donation of blood within 4 weeks of Day 1.
13. History of prolonged QT syndrome or a Screening QTc interval with Fridericia's correction (QTcF) > 450 msec for males or QTcF > 470 msec for females.
14. Females who are nursing, pregnant, or planning to become pregnant while in the study and for 4 weeks after the last dose of study medication.
15. History of meeting DSM-5 criteria for moderate to severe alcohol or substance use disorder (other than nicotine or caffeine) within the 6 months before the first Screening Visit (Week -5).
16. Positive alcohol breath test.

Note: A repeat alcohol breath test will be allowed within 48 hours of the first test only at the first Screening Visit (Week -5). The repeat test must be negative for inclusion in the study.

17. Positive urine test for drugs of abuse at the Screening/Qualification Visit (Week -5, -3; see [APPENDIX B](#)).

Note: Patients with a positive urine drug screen for benzodiazepines may be allowed in the study provided the drug was prescribed by a physician as an anxiolytic or sleep aid

Note: Use of THC/cannabinoid products is allowed in the study

18. Patients with positive blood screen for human immunodeficiency virus (HIV antibody) and/or hepatitis B virus surface antigen.

Note: Patients with asymptomatic hepatitis C are allowed as long as the clinical laboratory mentioned above requirements are met.

19. Patients with history of renal disease or those taking medications to treat renal disease.
20. Any other clinically significant medical condition (e.g. fever, active infection, uncontrolled diabetes, cardiovascular conditions including Class III or IV heart failure, pulmonary embolism, deep vein thrombosis, active major autoimmune disease, neurological disease, cancer not in remission for last 3 years except basal cell and squamous cell carcinoma), or procedure as determined by the Investigator, that may unfavorably alter the risk-benefit of study participation, adversely affect study compliance, or confound interpretation of study results.

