
9. If of reproductive age and not infertile (defined below), willing and able to use a medically highly effective form of birth control during the study and for 4 weeks following last dose of Study Medication. Examples of medically highly effective forms of birth control are:
 - a. Surgical sterility (via vasectomy, hysterectomy or bilateral ligation) or post-menopausal females (have had spontaneous amenorrhea for at least the last 1 year and at least 1 year after the onset of amenorrhea while not receiving hormone replacement therapy and have a Follicle-Stimulating Hormone (FSH) level greater than 40 mIU/mL)
 - b. Sexual partner is sterile, or of the same sex
 - c. Implants of levonorgestrel in females
 - d. Oral contraceptive (combined or progesterone only) in females
 - e. Double-barrier method (any combination of physical and chemical methods)
 - f. Intrauterine device in females, or other method with published data showing that the lowest expected failure rate is less than 1% per year
10. Healthy, as determined by the Investigator, based on a medical evaluation including history, physical examination, vital signs, electrocardiogram (ECGs) and clinical laboratory assessments at Week -5.

Note: A patient with a non-clinically significant abnormality or laboratory parameters outside the reference range may be included only if the Investigator considers that the finding will not

compromise the patient's safety and will not interfere with the study procedures or data interpretation.

11. Body mass index (BMI) within the range of 18 to 40 kg/m², inclusive, at the first Screening Visit (Week -5).

Exclusion Criteria:

1. Patients with DSM-V criteria at the first Screening Visit (Week -5) for disorders other than schizophrenia that in the opinion of the Investigator may interfere with study conduct and interpretation of results.
2. Patients who, in the opinion of the Investigator, have a history of antipsychotic treatment resistance.
3. Patients currently taking clozapine.
4. Patients who have been previously treated with or are receiving electroconvulsive therapy (ECT).
5. Patients who have initiated or changed dose of antidepressants or other moods stabilizers within 7 weeks prior to the first Screening Visit (Week -5).
6. Patients currently taking lithium.
7. Patients taking an AP (e.g. Seroquel) as a sleep aid.

Note: Patients will be allowed to switch to a non-AP sleep aid during the Screening period.

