7. INVESTIGATIONAL PLAN

7.1. Overall Study Design

This is a randomized, double-blind, parallel group, placebo-controlled, multicenter study. At screening, potential study participants must have a DSM-V diagnosis of schizophrenia for at least 2 years and confirmed by psychiatric evaluation and MINI. The study will involve patient participation for up to 20 weeks and will consist of a 5-week Screening/Qualification Period, a 12-week Treatment Period and a Safety Follow-Up Visit approximately 1 week after the last dose of Study Medication. The Qualification period may be extended up to 2 weeks (after Week -3, prior to Randomization) if repeat laboratory test results for confirmation of eligibility are pending. Approximately 300 patients, 18-55 years old, will be randomized to receive 1 g, 2 g or 4 g of CTP-692 or Placebo once-daily (QD). At the first Screening Visit (Week -5), patients will provide informed consent and will be assessed for eligibility based on study inclusion and exclusion criteria, including a total score of 70-110 on the Positive and Negative Syndrome Scale (PANSS). Patients meeting eligibility requirements at the first Screening Visit will undergo an additional in-clinic Qualification Visit (at Week -3). Patients who continue to meet eligibility criteria based on assessments at the Screening and Qualification visits and Day 1 will be randomized in a 1:1:1:1 ratio to 1 of the 4 treatment groups shown below in [Figure 1](#):

Figure 1: CP692.2001 Study Design

Note: The Qualification period may be extended up to 2 weeks (after Week -3, prior to Randomization) if repeat laboratory test results for confirmation of eligibility are pending.

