9. SELECTION AND WITHDRAWAL OF PATIENTS

9.1. Inclusion Criteria

1. Patient should be able to read, understand and voluntarily sign an informed consent document prior to any study related assessments and procedures being conducted. Patients should be willing to comply with the study visits and requirements of the study protocol.
2. Patient should be between 18 and 55 years of age, inclusive, at the time of signing the informed consent document.
3. Physician confirmed DSM-V diagnosis of schizophrenia for the past 2 years based on patient's history and confirmed by psychiatric evaluation and MINI International Neuropsychiatric Interview Psychotic Disorders, version 7.0.2 (MINI, Version 7.0.2; see [APPENDIX L](#)).
4. The patient is an outpatient with no hospitalization for worsening of schizophrenia within 3 months of the first Screening Visit (Week -5).
5. Patients currently treated with one antipsychotic (AP) medication which has been unchanged (medication and dose) for at least 7 weeks prior to the first Screening Visit (Week -5), and expected to remain unchanged during the Screening and Treatment period. Allowed orally dosed APs are:
 - a. Aripiprazole
 - b. Asenapine
 - c. Brexipiprazole
 - d. Cariprazine
 - e. Lurasidone
 - f. Olanzapine
 - g. Paliperidone
 - h. Quetiapine
 - i. Risperidone

Note: If the patient is being treated with depot or long-acting antipsychotics, they should be on the treatment for at least 2 drug administration cycles prior to the first Screening Visit (Week -5).

6. Patients with confirmed blood levels of their current AP medication in samples drawn at the Qualification Visit (Week -3).
7. The patient has a reliable informant who is able to provide information regarding the patient and support study participation.

8. Patients with clinically stable schizophrenia with residual symptoms defined as PANSS total score of 70-110 per evaluation at the first Screening Visit (Week -5), the Qualification Visit (Week -3) and Day 1.

Note: At Week -3 and Day 1, the PANSS total score may vary by 10 points as compared to a previous visit, as long as total score remains between 70-110 at each of the three visits for the patient to be included in the study.

Patients must also meet these additional PANSS criteria:

- a. PANSS score of ≤ 4 on positive scale items of conceptual disorganization and hostility
- b. PANSS score ≥ 4 on **at least two** of the following items:
 - a. Delusions
 - b. Hallucinations
 - c. Suspiciousness/Persecution

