10.4. Concomitant Medications and Procedures

All patients will be instructed to take their standard AP medication throughout the study. All medications, including the standard AP medication and over-the-counter therapies (e.g., vitamins, herbal, and nutritional supplements), taken at the time of the Screening Visit (Week -5 Visit) through the Follow-Up Visit will be recorded in the patient's source documentation and documented in the eCRF.

Any concomitant medication deemed necessary for the wellbeing of the patient may be given at the discretion of the Investigator. Use of medications that are prohibited per protocol may lead to patient withdrawal from the study.

A list of allowed and prohibited concomitant medications is shown in [APPENDIX A](#).

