18. APPENDICES

APPENDIX A: CONCOMITANT MEDICATIONS

ALLOWED MEDICATIONS	PROHIBITED MEDICATIONS
Antipsychotics Aripiprazole Asenapine Brexpiprazole Cariprazine Lurasidone Olanzapine Paliperidone Quetiapine Risperidone Contraceptives (oral and implants) Non-antipsychotic sleep medications	ADD prescription medications ADHD prescription medications Clozapine Lithium

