#### **5.1.5 Study Day and Visit Window Definitions**

The baseline assessment for all efficacy endpoints is defined as last assessment prior to the first dose of Study Medication on Day 1. Data obtained during unscheduled and at the Week 12/Early Termination early visits will be allocated to the scheduled time point corresponding to the visit window in which they fall in as specified in Table 2. For patients completing the study, data will be analyzed based on the nominal visits and nominal time points. If the data from the nominal visit or time point are missing or the patient did not complete the study, data from

unscheduled visits or the Week 12/Early Termination visit within the time interval for the same nominal visit or time point will be used. If multiple visits among unscheduled or Early Termination assessments fall in the same visit window or time point, the non-missing assessment closest to target time point will be selected for analysis. If multiple values are the same number of days away from the target study day, then the latter value will be used. In the unlikely event an unscheduled or Early Termination visit, associated with a particular visit window, falls either prior to the actual previous nominal visit date or after the subsequent nominal visit date, it will not be used. This is done simply to ensure the data assigned to particular analysis time points will not be out of sequence.

The first date on which patient received the Study Medication will be used as the Study Day 1. Study days for other visits will be calculated as follows:

- Before Study Day 1 visit: Study Day = date of assessment – date of Study Day 1
- On or after Study Day 1 visit: Study Day = date of assessment – date of Study Day 1 + 1

Last study date is the last visit date of any scheduled, unscheduled, or Early Termination visits. Last Study Day is calculated as:

- Last Study Day = last study date – date of Study Day 1 + 1

The target study days of Study Center Visits are summarized below.

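### Exclusion 5 does not cover antidepressant or mood-stabiliser changes between the first Screening Visit (Week -5) and Day 1, so the most recent changes before the PANSS baseline are allowed

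*Protocol*

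**What the plan says.** Exclusion 5 in Protocol section 9.2 removes "Patients who have initiated or changed dose of antidepressants or other mood stabilizers within 7 weeks prior to the first Screening Visit (Week -5". The Synopsis uses the same anchor, "within 7 weeks prior to the first Screening Visit (Week -5".

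Section 7.1 describes a "5-week Screening/Qualification Period, a 12-week Treatment Period" and adds that "The Qualification period may be extended up to 2 weeks (after Week -3, prior to Randomization", for pending repeat laboratory results. SAP section 5.1.5 fixes the reference point for efficacy: "The baseline assessment for all efficacy endpoints is defined as last assessment prior to the first dose of Study Medication on Day 1".

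For the antipsychotic, Inclusion 5 requires the same 7 weeks without change before Week -5, and also that the drug is "expected to remain unchanged during the Screening and Treatment period". Exclusion 5 has no such clause for antidepressants and other mood stabilisers.

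On other drugs, section 10.4 says: "Any concomitant medication deemed necessary for the wellbeing of the patient may be given at the discretion of the Investigator". The prohibited column of Appendix A lists ADD and ADHD prescription drugs, clozapine and lithium. Exclusion 6 separately removes anyone currently taking lithium.

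**The concern.** The purpose of Exclusion 5 is evidently to keep recent changes in these drugs from disturbing the PANSS. As worded, it screens out older changes, which have had more time to settle, and admits those closest to baseline. For these drugs the rule guarantees no period of stability at Day 1.

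The primary endpoint is change in PANSS total score from Day 1 to Week 12. That total includes anxiety, guilt feelings, tension, depression and motor retardation (items G2, G3, G4, G6 and G7 in Appendix C), which an antidepressant or mood stabiliser may plausibly move. A drug started shortly before Day 1 could act during the treatment period and add change unrelated to study treatment. The planned power leaves little room for extra variability.

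**Working it through.** **1. Timeline.** Inputs: a 7-week look-back (Exclusion 5), a 5-week Screening/Qualification Period and an extension of up to 2 weeks (section 7.1).

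| | Nominal | Full extension |
|---|---|---|
| Week -5 visit, weeks before Day 1 | 5 | 5 + 2 = 7 |
| Start of barred window, weeks before Day 1 | 7 + 5 = 12 | 7 + 7 = 14 |
| End of barred window, weeks before Day 1 | 5 | 7 |
| Uncovered interval up to Day 1 | 5 weeks | 7 weeks |
| Antipsychotic stability by Day 1 under Inclusion 5 | 12 weeks | 14 weeks |
| Guaranteed stability by Day 1 under Exclusion 5 | 0 weeks | 0 weeks |

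On the nominal schedule, a change 11 weeks before Day 1 lies inside the 12-to-5-week window and excludes. A start 1 week before Day 1 lies outside it and does not.

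**2. Does another provision close the interval?**

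- Inclusion 5: its forward-looking clause covers the antipsychotic only.
- Section 10.4 and Appendix A: antidepressants are not prohibited, and lithium is the only mood stabiliser listed.
- Eligibility checks at Week -3 and Day 1 (sections 8.2.1 and 8.2.2): these re-apply a criterion that still looks back from Week -5. The accompanying medication review names stability only for antipsychotic therapy.
- Withdrawal criteria (section 9.3): no mention of such a change.
- Per-Protocol Population (SAP 5.1.2.4): it removes major eligibility deviations, but this patient has breached no criterion.

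None of them closes it.

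**3. The plan's own power.** Section 13.1 gives 60 completers per arm, a difference of 5.2, SD 10 and a two-sided t-test at 0.05.

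Noncentrality = 5.2 / (10 × √(2/60)) = 2.848, with 118 degrees of freedom and critical value 1.980. Power is **80.6%** (81.3% by the normal approximation). The stated figure of at least 80% is reproduced.

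**4. Illustration of size.** Assume a fraction f of patients in every arm start or change such a drug shortly before Day 1, and that their PANSS change shifts by s points after baseline. Neither value is in the documents. The added variance is f(1 − f)s², so SD = √(100 + f(1 − f)s²).

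| f | s | Variance | SD | Power at 60 per arm |
|---|---|---|---|---|
| none | none | 100 | 10.00 | 80.6% |
| 5% | 6 | 100 + 0.0475 × 36 = 101.71 | 10.09 | 80.0% |
| 10% | 8 | 100 + 0.09 × 64 = 105.76 | 10.28 | 78.4% |
| 15% | 10 | 100 + 0.1275 × 100 = 112.75 | 10.62 | 75.8% |

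**The case against.** The main background treatment is well protected. The antipsychotic must be unchanged for 7 weeks before Week -5, is expected to stay so, and is confirmed by blood level at Week -3 (Inclusion 6). Lithium is barred. Only patients who change another such drug during Screening are affected. This stands, and it limits the point. A reader might infer that baseline is generally taken on an unstable background; the documents do not support that.

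There are also partial safeguards. PANSS total must lie within 70-110 at three visits, with a note on 10-point variation. The Investigator may exclude interfering comorbid disorders (Exclusion 1) and may withdraw a patient when data integrity is at risk. The SAP adds an exploratory PANSS change from the average of the three pre-dose assessments. These reduce the risk, but none bars the change, and a PANSS rule applied up to Day 1 cannot detect an effect that emerges later.

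A reader might also infer a raised placebo response that distorts the treatment effect. That does not follow. The changes precede randomisation and balance across arms in expectation, so a shift equal in all arms leaves the difference from placebo unaltered.

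The power figures are open to fair criticism. The rates are assumed, and the top case gives 15% of patients a shift nearly twice the planned effect of 5.2. The planned SD of 10 may already include ordinary background changes. A drug started early in Screening may act partly before Day 1. The calculation is a completer t-test, whereas the primary analysis is a baseline-adjusted MMRM. At the low end the loss is about half a percentage point.

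**Conclusion.** The gap is real, but narrow. Exclusion 5 leaves the whole interval from Week -5 to Day 1 uncovered for antidepressants and for mood stabilisers other than lithium, and no other provision fills it. It is an omission in the wording, not a contradiction between passages.

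The consequence is added variability in PANSS change, not bias in the active-placebo contrast. Its size cannot be determined from the documents. Under the assumed 5-15% of patients shifting 6-10 points, equally in all arms and wholly after baseline, the loss of power runs from about 0.6 to 4.8 percentage points. These figures show scale only. They do not call the planned sample size into question, since the stated power reproduces. The case for acting rests on the low cost of the correction and on a rule that, as written, admits the changes closest to baseline.

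**What to change.** Amend Exclusion 5 in both the Synopsis and section 9.2 so that its window runs from 7 weeks before the first Screening Visit through Day 1. Its coverage of Screening would then be consistent with the antipsychotic rule in Inclusion 5. The two would not be identical: Inclusion 5 states an expectation, while this would be a bar on entry. The change concerns eligibility only.

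The cost is one line, in two places, in an amendment. The downside is a few more screen failures among patients whose antidepressant or mood stabiliser is started or adjusted during Screening. No new assessment is needed, because concomitant medications are already reviewed at Week -3 and Day 1. The amendment can help only patients not yet randomised.

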9.3. Patient Withdrawal Criteria

Patients may withdraw from participation in the study at any time. The Investigator may withdraw a patient at any time if they believe the safety of the patient or the integrity of the data are at risk. In addition, patients should be withdrawn if they:

- Experience a serious or intolerable AE
- Develop a clinically significant laboratory or ECG abnormality
- Develop proteinuria of 1-2+ or UACR > 30 mg/g as confirmed by a repeat lab test
- Develop eGFR levels < 60 mL/minute/1.73 m² as confirmed by a repeat lab test
- Develop *symptomatic* ALT or AST elevation ≥ 2 x the ULN on two repeat lab tests or develop *asymptomatic* ALT or AST elevation ≥ 3 x the ULN as confirmed by a repeat lab test
- Develop total bilirubin ≥ 2 x the ULN as confirmed by a repeat lab test
- Exhibit suicidal behavior as determined by an affirmative answer on items 4 or 5 on the C-SSRS
- Do not follow guidelines specified in the protocol (i.e., is noncompliant with protocol procedures or Study Medication administration) or specific instructions by the study staff
- Any medically appropriate reason or significant protocol violation, in the opinion of the Investigator
- Are lost to follow up

In case of two consecutive missed safety assessments due to the COVID-19 pandemic, continued patient participation in the study must be discussed by the Investigator and the Medical Monitor.

